- *Motor nerves* control movements of all muscles under conscious control, such as those used for walking, grasping things, or talking

- *Sensory nerves* transmit information about sensory experiences, such as the feeling of a light touch or the pain resulting from a cut.
- *Autonomic nerves* regulate biological activities that people do not control consciously, such as breathing, digesting food, and heart and gland functions.

➤ Forms of Neuropathy

- *Mononeuropathies*: Neuropathies that involve damage to only one nerve.
- *Polyneuropathies*: Neuropathies that involve multiple nerves affecting all limbs.
- *Mononeuritis multiplex*: Less commonly, neuropathies wherein two or more isolated nerves in separate areas of the body are affected

Some neuropathies affect all three types of nerves, but most often, neuropathies primarily affect one or two types. Therefore, neuropathies may be further described as predominantly motor neuropathy, predominantly sensory neuropathy, sensory-motor neuropathy, or autonomic neuropathy.

➤ Acute versus Chronic Neuropathies

In *acute neuropathies*, such as Guillain-Barré syndrome, symptoms appear suddenly, progress rapidly, and resolve slowly as damaged nerves heal.

In *chronic neuropathies*, symptoms begin subtly and progress slowly. There may be periods of relief followed by relapse. A plateau stage may be reached where symptoms stay the same for months or years. Some chronic neuropathies worsen over time, but fatality from neuropathy is extremely rare unless complicated by other diseases. Occasionally, neuropathy is a symptom of another disorder.

➤ Acquired peripheral neuropathies

Peripheral neuropathy may be either acquired or inherited.

➤ Acquired vs. inherited peripheral neuropathies

- *Acquired peripheral neuropathies* are grouped into three broad categories; those caused by:
 - ✓ *systemic disease*
 - ✓ *trauma from external agents*
 - ✓ *infections or autoimmune disorders affecting nerve tissue*

Causes of *acquired peripheral neuropathy* include:

- ✓ physical injury (trauma) to a nerve
- ✓ tumors
- ✓ toxins
- ✓ autoimmune responses
- ✓ nutritional deficiencies
- ✓ alcoholism
- ✓ vascular and metabolic disorders

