Previous, Over the Counter (OTC) use of the Erchonia laser has been proven in a lay person (non-doctor) usability and efficacy clinical trial which received FDA OTC clearance under 510(k) # **K162578 and K143007**. In this clinical study the lay person was provided a device operational manual for guidance on the treatment protocol and administration, no training was provided by the study sponsor.

Results showed device operation by the lay persons achieved equal or greater circumference reduction (6.2”) compared to the device administration from a licensed physician (3.54”), in the previous prescription-based FDA study using the identical device. Thus, proving the lay person’s ability to safely and correctly administer the Erchonia laser treatment.

STUDY DESIGN

This pilot study is a non-blinded, single group evaluation of the effect of the Erchonia® EVRL OTC™ on providing relief from chronic pain arising from diabetic peripheral neuropathy.

SUBJECT GROUP

All subjects will be test subjects; that is, all study subjects will receive the active Erchonia® EVRL OTC laser treatment.

NON-BLINDED DESIGN

This pilot study will be non-blinded, such that both subjects and the investigator(s) will be aware that they are receiving the study procedures with active (true) Erchonia® EVRL OTC laser device.

NON-RANDOMIZED

This pilot study is a non-randomized design, wherein all subjects receive the active procedure administrations and the same treatment protocol.

COMPENSATION

A subject will not receive financial compensation for his or her participation in this clinical study.

A subject will not be charged for the cost of the study procedures with the Erchonia® EVRL OTC™ Laser or for the cost of any other directly related evaluations or measurements that occur as part of his or her participation in the study.

SAMPLE SIZE

There will be 10 qualified subjects enrolled in this pilot study.

STUDY PROCEDURE

STUDY TEST BATTERY

The following is a list and description of the study assessment tools to be used and the variables to be recorded in this clinical study. At each evaluation point, the precise tools and variables from this list that will be employed will be specified.

BASELINE VARIABLES

A. Neuropathy Variables

- Number of months/years since onset of foot pain.
- Number of months/years since diabetes diagnosis
- Insulin dependency

B. Medication and Treatment

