The pre-procedure evaluation phase commences following the delivery of the Erchonia® EVRL OTC™ device to the subject. During pre-procedure evaluation, the following is recorded over videoconference or telemedicine:

BASELINE VARIABLES

- Baseline Foot Variables
- Baseline Concomitant Medication and Therapy Use
- Subject Demographics

PRE-PROCEDURE OUTCOME ASSESSMENTS

- Numerical rating scale: Foot pain

PROCEDURE ADMINISTRATION PROTOCOL

- The procedure administration phase of the study commences following completion of the pre-procedure phase, on the same day or up to 15 days later.
- The procedure administration phase extends over 3 consecutive weeks.

ERCHONIA® EVRL OTC™ DIABETIC PERIPHERAL NEUROPATHY FOOT PAIN PILOT STUDY:
Study Protocol

- Each subject receives 42 total procedures with the Erchonia® EVRL OTC™: twice daily procedure administrations for 3 weeks.
- Each procedure administration lasts 10 minutes.
- Each procedure administration is completed at the subject's home.
- Each subject will be provided a "Operation Manual" that details the laser use and treatment administration.
- Each subject will be provided a "Treatment Log Form" to document each time the treatment is administered.

➤ **Procedure administration protocol is as follows:**

1. The subject seats comfortably in a chair and is correctly fitted with the provided safety goggles.
2. The Erchonia® EVRL OTC™ laser is held at the top of the right foot, at a distance of approximately 3-6 inches from the skin throughout the entire treatment.

Note: The laser lights will cover the top of ankle joint and beyond the toes. (*shown in Fig 2*)

[figure not shown]

Fig 1. Treatment

Fig 2. Treatment Close Up

3. The Erchonia® EVRL OTC™ is then activated for 5 minutes.
4. Step 2-3 is then repeated over the left foot. Both the right and left foot will receive 5-minute treatment each.
5. The subject's protective eyewear is then removed, and the session is over.

PROCEDURE ADMINISTRATION PHASE MEASURES

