1 WEEK EVALUATION

Following 1 week of study procedure administrations with the Erchonia® EVRL OTC™, the following will be recorded over phone call or videoconference with the investigator and subject:

- Numerical rating scale: Foot pain
- Adverse Events Evaluation

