3 WEEK EVALUATION: STUDY ENDPOINT

Following 3 weeks of study procedure administrations with the Erchonia® EVRL OTC™, the following will be recorded over phone call or videoconference with the investigator and subject as outlined in the STUDY TEST BATTERY section above. These recordings will form the study endpoint data set from which change from baseline will be evaluated with respect to assessing study outcome.

- Numerical rating scale: Foot pain
- Subject Satisfaction with Study Outcome
- Adverse Events Evaluation

POST- TREATMENT EVALUATION PHASE

WEEK 7: POST TREATMENT FOLLOWUP

Four weeks following completion of the 3-week Treatment Phase (7 weeks after study onset), the following will be recorded over phone call or videoconference with the investigator and subject:

- Numerical rating scale: Foot pain
- Subject Satisfaction with Study Outcome
- Adverse Events Evaluation

ADVERSE EVENTS

At any time throughout the duration of the clinical trial that is necessary, any and all potential adverse events reported by a subject will be reported to the investigator and will be recorded on the case report form, and subsequently evaluated by a suitably qualified independent reviewer for determination of relationship to the study treatment and whether

or not any corrective action needs to be taken. All potential adverse events recorded will be appropriately reported to the governing IRB, as applicable.

It is unlikely and not expected that any adverse events will result from implementation of this clinical study protocol. Prior clinical trials using low level laser light have not typically yielded any adverse events or reactions. However, potential adverse events that may feasibly occur from application of the Erchonia® EVRL OTC™ include, but are not necessarily limited to: skin irritation, discoloring, rash, indentations and infection.

PRIVACY AND CONFIDENTIALITY

Records for each subject in this clinical study will be maintained in separate files in a locked filing cabinet at the Investigators site. The investigator will be responsible for ensuring that all records for a subject pertaining to his or her participation in the clinical study are maintained in the subject's file at all times other than when information is being recorded on them.

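### The only pre-procedure pain score may be up to 15 days old when treatment starts and is not repeated, so pain change in that gap, in either direction, enters the change from baseline

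*Protocol*

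**What the plan says.** Under PRE-PROCEDURE EVALUATION PHASE, the protocol sets the timing of this phase: "The pre-procedure evaluation phase commences following the delivery of the Erchonia® EVRL OTC™ device to the subject". It then introduces the data to be collected: "During pre-procedure evaluation, the following is recorded over videoconference or telemedicine". The list holds the baseline variables and one NRS for foot pain. The protocol never states in words which score is the baseline, but this one is recorded alongside the baseline variables and is the natural reading.

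PROCEDURE ADMINISTRATION PROTOCOL allows a gap before treatment: "The procedure administration phase of the study commences following completion of the pre-procedure phase, on the same day or up to 15 days later". On the length of treatment it says: "The procedure administration phase extends over 3 consecutive weeks".

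No NRS is listed at the first session. The next rating is in 1 WEEK EVALUATION: "Following 1 week of study procedure administrations with the Erchonia® EVRL OTC™". Further ratings follow after weeks 2 and 3 of treatment and at week 7.

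On the week 3 data, 3 WEEK EVALUATION: STUDY ENDPOINT says: "These recordings will form the study endpoint data set from which change from baseline will be evaluated with respect to assessing study outcome". STUDY DESIGN describes the trial as follows: "This pilot study is a non-blinded, single group evaluation of the effect of the Erchonia® EVRL OTC™". SAMPLE SIZE gives 10 subjects.

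One other pre-treatment score exists. INCLUSION CRITERIA PART 1 requires an NRS of at least 50, and it is applied before the device is shipped.

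**The concern.** In a single-group study the before-after change is the whole estimate. If the before score is taken some days ahead of treatment, the change score mixes what happened under treatment with what happened while the subject was waiting. With no control group, nothing separates the two.

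The wait may also differ between subjects, from none to 15 days, so the 10 change scores do not cover the same interval. A fall in pain during the wait makes the device look better; a rise makes it look worse.

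The documents do not let one predict which. Of chronic neuropathies in general, the protocol says: "There may be periods of relief followed by relapse. A plateau stage may be reached where symptoms stay the same for months or years". A change in pain medication could also fall inside the gap for some subjects, because the eligibility criteria ask for restraint during participation without tying its start to the baseline rating.

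The Treatment Log Form can show how long each gap was. No later analysis can recover a first-day score that was never collected.

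**Working it through.** The protocol states no figure to reproduce: it gives no sample size calculation, and STATISTICAL ANALYSIS plans no analysis. The check is timeline arithmetic.

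**Inputs**
- Gap g from the pre-procedure phase to the first session: 0 to 15 days (PROCEDURE ADMINISTRATION PROTOCOL).
- Ratings after 7, 14 and 21 days of treatment (the 1, 2 and 3 week evaluations).
- Follow-up four weeks after the 3-week phase: 21 + 28 = 49 days from the first session (WEEK 7: POST TREATMENT FOLLOWUP). The protocol calls this 7 weeks after study onset, so its clock starts at the first session, not at the baseline call.

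**What the change score contains**

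Let Yb be the pre-procedure score, Y0 the unrecorded score just before the first session, and Y3 the week 3 score. Then

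Y3 − Yb = (Y3 − Y0) + (Y0 − Yb).

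The second term is the change during the gap. It is zero by construction only for a same-day start.

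**Intervals.** Days from baseline = g + days since the first session. Pre-treatment share = g / (days from baseline).

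| Rating | g = 0 | g = 7 | g = 15 | Pre-treatment share at g = 15 |
|---|---|---|---|---|
| Week 1 | 7 | 14 | 22 | 15/22 = 68% |
| Week 2 | 14 | 21 | 29 | 15/29 = 52% |
| Week 3 (endpoint) | 21 | 28 | 36 | 15/36 = 42% |
| Week 7 | 49 | 56 | 64 | 15/64 = 23% |

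At g = 7 the share is 7/28 = 25% for week 3 and 7/14 = 50% for week 1. At g = 0 it is 0%.

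**Conversion to points.** For drift of d points per week, the shift in a subject's change score is d × g/7. With d = 1 and g = 15 this is 15/7 = 2.1 points on the 1 to 100 scale, in the direction of the drift.

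**Illustrations under assumed values** (the documents give neither a drift rate nor a standard deviation)
- Mean drift between −10 and +10 points over a full 15 days, linear in time: the mean change shifts by up to 10 × 7.5/15 = 5 points either way at a mean gap of 7.5 days, and by up to 10 points at 15 days.
- Zero mean drift, but a between-subject SD of 5, 10 or 15 points for the gap change: the standard error component in the mean of 10 is SD/√10 = 1.6, 3.2 or 4.7 points.

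**The eligibility score.** It precedes shipment, and the pre-procedure call follows delivery, so it lies further from treatment. Using it as baseline would lengthen the gap.

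**The case against.** The strongest case against concerns weight. This is an openly declared exploratory pilot of 10 subjects, with no planned statistical analysis, no pre-established outcome measures and no success criteria. No test or decision rule is distorted. That stands, and it limits the consequence to the descriptive results. Those results may, however, help develop a controlled study, and change from baseline is how the protocol says outcome is assessed.

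Second, every share quoted at 15 days is an upper limit. A same-day start is allowed, the device is already delivered when the call is held, and no typical gap is stated. That stands too; actual gaps may be short.

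Third, subjects must have had constant foot pain for at least three months, and the protocol describes chronic neuropathy as progressing slowly. This weakens the expectation of large drift. But pain that is constantly present need not be constant in severity, and the same section describes relief and relapse.

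Fourth, treatment exposure is not mixed: the ratings are tied to weeks of treatment, so only the age of the baseline differs. That is correct, and it is the point at issue.

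Finally, drift during the three treated weeks stays confounded whatever is done. That is true of any single-group design. The gap adds a further component that is unequal between subjects and avoidable.

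**Conclusion.** The concern holds. The protocol allows the only pre-procedure score to be up to 15 days old at the first session, repeats no score before treatment, and judges outcome by change from baseline without a control. Pain change in the gap therefore enters the result. At the limit, 15 of the 36 days to the endpoint precede treatment (42%), and 15 of the 22 days to week 1 (68%).

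This rests on reading the pre-procedure NRS as the baseline and on counting the 15 days from the day of that score. If the pre-procedure phase takes more than one day, the score could be slightly older. The direction and size of any bias cannot be derived from the documents; the only firm conversion is 2.1 points for each 1 point per week of drift over a full gap. No formal inference is affected. The change is worth making because it is cheap and the score cannot be obtained afterwards.

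**What to change.** Record one NRS on the day of the first procedure, before the first session, by the same phone or video call method as the other ratings; or hold the pre-procedure call on that day. Define that score as the baseline for all change scores. Keep the eligibility score and any earlier pre-procedure score to document eligibility and to describe pre-treatment drift, which would itself help in designing the controlled study. The 15-day allowance can stay.

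The nominal interval from baseline to week 3 is then 21 days for every subject, with a pre-treatment share of 0%. It is nominal because the protocol sets no window around the evaluation calls. Drift during the three treatment weeks is not removed.

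The cost is at most one short call and one rating per subject, 10 in total, and none for those who start on the day of the pre-procedure call and are rated before the first session. A small wording change is needed in the protocol and the case report form. No treatment rule changes.

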1 WEEK EVALUATION

Following 1 week of study procedure administrations with the Erchonia® EVRL OTC™, the following will be recorded over phone call or videoconference with the investigator and subject:

- Numerical rating scale: Foot pain
- Adverse Events Evaluation

2 WEEK EVALUATION

Following 2 weeks of study procedure administrations with the Erchonia® EVRL OTC™, the following will be recorded over phone call or videoconference with the investigator and subject:

- Numerical rating scale: Foot pain
- Adverse Events Evaluation

3 WEEK EVALUATION: STUDY ENDPOINT

Following 3 weeks of study procedure administrations with the Erchonia® EVRL OTC™, the following will be recorded over phone call or videoconference with the investigator and subject as outlined in the STUDY TEST BATTERY section above. These recordings will form the study endpoint data set from which change from baseline will be evaluated with respect to assessing study outcome.

- Numerical rating scale: Foot pain
- Subject Satisfaction with Study Outcome
- Adverse Events Evaluation

POST- TREATMENT EVALUATION PHASE

WEEK 7: POST TREATMENT FOLLOWUP

Four weeks following completion of the 3-week Treatment Phase (7 weeks after study onset), the following will be recorded over phone call or videoconference with the investigator and subject:

- Numerical rating scale: Foot pain
- Subject Satisfaction with Study Outcome
- Adverse Events Evaluation

ADVERSE EVENTS

At any time throughout the duration of the clinical trial that is necessary, any and all potential adverse events reported by a subject will be reported to the investigator and will be recorded on the case report form, and subsequently evaluated by a suitably qualified independent reviewer for determination of relationship to the study treatment and whether

or not any corrective action needs to be taken. All potential adverse events recorded will be appropriately reported to the governing IRB, as applicable.

It is unlikely and not expected that any adverse events will result from implementation of this clinical study protocol. Prior clinical trials using low level laser light have not typically yielded any adverse events or reactions. However, potential adverse events that may feasibly occur from application of the Erchonia® EVRL OTC™ include, but are not necessarily limited to: skin irritation, discoloring, rash, indentations and infection.

PRIVACY AND CONFIDENTIALITY

Records for each subject in this clinical study will be maintained in separate files in a locked filing cabinet at the Investigators site. The investigator will be responsible for ensuring that all records for a subject pertaining to his or her participation in the clinical study are maintained in the subject's file at all times other than when information is being recorded on them.

Copies of all subject case report forms will be made and supplied to Regulatory Insight, Inc. Regulatory Insight, Inc. will maintain these copies in a separate clinical study file that is kept in a locked filing cabinet on their respective premises. The original records will be maintained at the respective test site.

Subjects' identities will be kept confidential by assigning each subject a subject ID upon acceptance into the study. The subject ID will comprise the investigator's two initials (first and last name initials) and a three-digit number that will be based upon the subject's order of entry into the clinical study. For example, with Investigator [name] would have a subject ID of JB101-JB110. Regulatory Insight, Inc. will receive no additional identifying information about a subject and will therefore have no way of linking a subject ID to a particular subject and his or her results.

MONITORING OF THE CLINICAL STUDY

Prior to commencement of the study, the trained study Monitor(s) will provide formalized and documented training to the conduct of clinical studies in general, to the specifics of the current clinical study protocol, to the identification and reporting of adverse events and protocol deviations and to the correct set-up, operation and treatment application of the Erchonia® EVRL OTC to the study population for all involved parties. A formalized Clinical Trial Monitoring Plan will be in place that will be strictly followed to ensure on-going compliance and accuracy of procedures.

STATISTICAL ANALYSIS

No Statistical Analysis. As this is an observational pilot study only, there are no pre-established primary or secondary outcome measures and no pre-established individual subject or study success criteria; rather it is the goal of this study to explore the potential benefits of low level laser therapy administration with the Erchonia EVRL OTC™ in reducing chronic pain associated with peripheral neuropathy, the results of which may be used to assist in developing a controlled clinical study to formally evaluate the study goal in the future.

END OF DOCUMENT
